### **(5)research method**

Subjects were recruited from patients with septic shock admitted to the Emergency Department of Guangzhou Panyu District Central Hospital between December 2022 and January 2026. Demographic data of patients, including gender, age, and underlying diseases, were collected, along with mean arterial pressure, baseline lactate levels, and vital signs at enrollment. Records were made of the total fluid volume administered within the first 6 hours after patients were randomized into groups, the achievement of resuscitation targets, blood lactate levels, blood pressure, and the incidence of complications such as pulmonary edema and renal injury. Additionally, the use of vasoactive agents (e.g., dopamine, epinephrine/norepinephrine), mechanical ventilation support, and antibiotics was documented. Patients were followed up to record the duration of Emergency Department stay, total hospital stay, 28-day mortality, and adverse events occurring during the study period (e.g., severe arrhythmias, anaphylactic shock).

### **(6) Observation items and detection time points**

1. Demographic data of patients, including gender, age, and underlying diseases, were collected, along with mean arterial pressure, baseline lactate levels, and vital signs at enrollment.
2. Records were made of the total fluid volume administered within the first 6 hours after patients were randomized into groups, the achievement of resuscitation targets, blood

lactate levels, blood pressure, and the incidence of complications such as pulmonary edema and renal injury.

3. Document the use of vasoactive agents (e.g., dopamine, epinephrine/norepinephrine), mechanical ventilation support, and antibiotics.
4. Record the duration of Emergency Department stay, total hospital stay, 28-day mortality, and adverse events occurring during the study period (e.g., severe arrhythmias, anaphylactic shock).

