#### **(4) case selection**

##### 1. Inclusion criteria:

(1) diagnosis of septic shock in accordance with the Surviving Sepsis Campaign International; (2) receipt of initial fluid resuscitation in the emergency department with a hospital stay of at least 6 hours; (3) age  $\geq 18$  years; (4) provision of informed consent.

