## **(10)Statistical processing**

This study adopted a prospective randomized controlled design, and the sample size was estimated using PASS 15.0 software. Based on the difference in 6-hour fluid resuscitation volume between the two groups in the pilot study (mean difference 1261 mL, standard deviation 3155 mL),  $\alpha=0.05$  (bilateral) was set  $\beta=0.2$ , Calculated to require 27 cases per group, considering a 20% dropout rate, 60 cases were ultimately included. Use SPSS 26.0 to generate block random sequences (block size 4), and allocate concepts through sealed envelopes. The normality of the measurement data was confirmed by Shapiro Wilk test, and those that conform to the normal distribution were expressed as mean  $\pm$  standard deviation. Independent sample t-test was used for inter group comparison; non normally distributed individuals are represented by the median (interquartile range) and Mann Whitney U test is used. The categorical data is presented in terms of the number of cases (%), and the comparison between groups is conducted using the chi square test or Fishers exact test (when the theoretical frequency is less than 5). The main outcome (28 day mortality rate) was plotted using Kaplan Meier survival curve, and inter group differences were analyzed using log rank test, and HR (95% CI) was calculated. Secondary outcomes (such as fluid dosage, MAP, etc.) report mean difference (MD) or relative risk (RR) and their 95% confidence intervals. All tests are bilateral, and  $P<0.05$  is considered statistically significant. Perform Bonferroni correction on secondary outcomes ( $\alpha=0.05/6 \approx 0.008$ ). Multivariate Cox regression was used to adjust for confounding factors such as age and baseline lactate, and sensitivity analysis included protocol set (PP) and intention to treat (ITT) analyses. The statistical software used is R 4.3.1 (R Foundation) and SPSS 26.0 (IBM).

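### Body weight and fluid given before randomisation are not listed at enrolment, and 6-hour volume is compared unadjusted in raw mL, so the outcome that sizes the trial may carry avoidable variance.

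*Protocol*

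**What the plan says.** The trial is sized on fluid volume. Section (10) of the Protocol starts "Based on the difference in 6-hour fluid resuscitation volume between the two groups in the pilot study", with inputs "mean difference 1261 mL, standard deviation 3155 mL", and concludes: "Calculated to require 27 cases per group, considering a 20% dropout rate, 60 cases were ultimately included". The scale is millilitres throughout; no mL/kg scale appears.

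For analysis, section (10) states: "Independent sample t-test was used for inter group comparison", with Mann-Whitney U where the data are not normal. Fluid volume is named there as a secondary outcome, reported as a mean difference, and secondary outcomes carry a Bonferroni level of 0.05/6. The only covariate adjustment named is a Cox model with covariates such as age and baseline lactate, which does not apply to a volume. Randomisation is in blocks of 4, with no stratification factor named.

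The enrolment data in section (6) are demographic items "including gender, age, and underlying diseases, were collected, along with mean arterial pressure, baseline lactate levels, and vital signs at enrollment". The same list stands in the synopsis (research design row), section (3) and section (5). None of the four names body weight or fluid already given.

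The inclusion criteria in section (4) require "receipt of initial fluid resuscitation in the emergency department" together with a hospital stay of at least 6 hours.

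The outcome window has two definitions. Section (6), like the synopsis design row and sections (3) and (5), records the "total fluid volume administered within the first 6 hours after patients were randomized into groups". The efficacy row of the synopsis counts the 6 hours from resuscitation instead.

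**The concern.** How many millilitres a patient receives after randomisation plausibly depends on body size and on how much was given beforehand, whichever monitor guides treatment. Adults of any weight are eligible, and the inclusion criterion suggests that at least some patients will have had fluid before allocation. If so, both quantities add spread to the volume that has nothing to do with the monitor.

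The planning SD is already 2.5 times the planned difference (3155/1261 = 2.50). With about 30 per group and no stratification, chance differences in either quantity feed into the estimate. Adjustment could take some of this out, but the Protocol neither lists the values nor plans to adjust volume for anything. What is at stake is the width of the confidence interval for the outcome most directly tied to the monitoring method.

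**Working it through.** **Inputs.** From section (10): difference 1261 mL, SD 3155 mL, two-sided alpha 0.05, power 80%, Bonferroni level 0.05/6. From the synopsis: 30 per group. (Section (3) speaks of 73 participants; I use the 60 of the synopsis and section (10).) Assumed, because the documents give nothing: the share of variance R² that weight and prior fluid explain together, taken as 10%, 20% and 30%.

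**The plan's own figure.** n per group = 2 × (1.960 + 0.842)² × (3155/1261)² = 2 × 7.849 × 6.260 = 98.3, so 99; the t-based count is 100. The stated 27 is not reproduced. A one-sided test gives 78 to 79, a paired or one-sample formula gives 50, and SD/√2 gives 50 to 51. Only halving the SD comes near (25 to 26), and that is not a standard variant. A 20% dropout allowance on 27 would also give 27/0.8 = 33.75, so 34 per group, not 30. This is a separate fault, but it fixes the baseline for what follows.

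**Unadjusted test.** Standardised difference d = 1261/3155 = 0.400. Standard error = 3155 × √(2/30) = 815 mL, and the 95% half-width = 2.002 × 815 = 1631 mL. Noncentrality = 0.400 × √(30/2) = 1.548 on 58 degrees of freedom. Power is 33% at 0.05 and 13% at 0.05/6.

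**With adjustment.** Residual SD = 3155 × √(1 − R²). Power is computed as above with the residual SD, and the equivalent unadjusted sample is 30/(1 − R²). The two degrees of freedom spent on covariates are ignored; the effect is negligible.

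| Assumed R² | Residual SD (mL) | 95% half-width (mL) | Power at 0.05 | Power at 0.05/6 | Equivalent n per group |
|---|---|---|---|---|---|
| 0 | 3155 | 1631 | 33% | 13% | 30 |
| 10% | 2993 | 1547 | 36% | 15% | 33 |
| 20% | 2822 | 1458 | 40% | 17% | 38 |
| 30% | 2640 | 1364 | 44% | 20% | 43 |

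These are before dropout. With 20% lost (24 per group), the unadjusted figures fall to 27% and 10%.

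**How much could weight alone explain?** Suppose volume were proportional to weight, with weight CV c and mean volume m. The share of variance would be (c × m/3155)². For assumed c of 15% to 25% and m of 2000 to 4000 mL this runs from (300/3155)² = 0.9% to (1000/3155)² = 10%. The upper rows of the table would therefore need a substantial contribution from prior fluid.

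**Could adjustment rescue the sample size?** For 80% power at 30 per group and alpha 0.05, the residual SD must be at most 1261 × √15/2.802 = 1743 mL, so R² = 1 − (1743/3155)² = 0.69. No value in the assumed range comes near that.

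**The case against.** Several points can be made for the plan, and some of them stand.

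*An unadjusted comparison of randomised groups is valid.* This stands. A chance imbalance in weight or prior fluid is already covered by the confidence interval. A reader might infer that the volume comparison is biased or confounded; the documents do not support that.

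*The values may be recorded anyway.* A reader might infer that they will never be available and that the loss cannot be made good. That goes too far. The demographic list is open-ended, and the emergency chart would be expected to hold both items. The supportable statement is that they are not listed.

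*Prior fluid may be no separate quantity.* A reader might take the inclusion criterion to mean that every patient has had fluid before randomisation. It does not prove this. It is joined to a stay of at least 6 hours, which is normally known only afterwards, so it can also describe the resuscitation that the trial guides; section (3) starts monitoring straight after enrolment. Under the synopsis window, some fluid given before randomisation would count in the outcome itself. This stands as far as the window must be reconciled first. Either way, recording the earlier volume is what allows it to be separated from fluid given under the assigned monitor.

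*Covariate choice belongs in the SAP.* Partly right. A SAP not shown here could add covariates. But the list of items to collect is protocol content, and section (10) already commits to an unadjusted test.

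*Fluid volume is not primary.* Correct: sections (7) and (10) name 28-day mortality, and the synopsis efficacy row names lengths of stay. It follows that 0.05/6 is the relevant level for this outcome and that the absolute gain is smaller there. Volume is nonetheless the outcome on which the trial was sized.

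**Conclusion.** The point holds as a minor design improvement. Two baseline quantities likely to influence the 6-hour volume are not listed, and the stated analysis is unadjusted in raw mL, so the outcome may carry avoidable variance.

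The size rests on assumed R² values. Over 10% to 30%, power gains 3 to 11 percentage points at 0.05 and about 2 to 7 at 0.05/6, and the confidence interval narrows by 5% to 16% (√0.9 = 0.949; √0.7 = 0.837). The figures assume the t-test branch, 30 analysed per group and the planning SD; under Mann-Whitney they are only approximate.

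A reader might hope that adjustment makes the planned 60 patients sufficient. It does not: the stated inputs need about 100 per group for 80% power at 0.05, and the sample-size statement has to be corrected in its own right.

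**What to change.** 1. Reconcile the outcome window between the synopsis efficacy row (from resuscitation) and the synopsis design row and sections (3), (5) and (6) (from randomisation). The analysis in step 3 needs volume counted from randomisation.
2. Add body weight, marked as measured or estimated, and any fluid volume given before randomisation to the enrolment items in the synopsis, section (3), section (5) and section (6). Both can be taken from the emergency chart; enter zero where no fluid was given.
3. In section (10), state that the 6-hour post-randomisation volume is analysed by ANCOVA with treatment group, body weight and pre-randomisation volume, and report the adjusted mean difference with its 95% CI. This keeps the mean difference that section (10) already promises.

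Cost: two form fields and a few lines of text, with no added enrolment. Some weights will be estimates; that reduces the gain in precision but does not bias the comparison.

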## **(7) standards for efficacy appraisal**

The primary outcome was 28-day mortality

Secondary outcomes included the efficacy of initial resuscitation, duration of hospital stay, incidence of complications, and other relevant parameters.

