| case selection      | 
Inclusion criteria:
 
(1) diagnosis of septic shock in accordance with the Surviving Sepsis Campaign International; (2) receipt of initial fluid resuscitation in the emergency department with a hospital stay of at least 6 hours; (3) age <math>\geq</math> 18 years; (4) provision of informed consent.
 
excluded criteria:
 
(1) contraindications to rapid fluid administration (e.g., end-stage renal disease, end-stage heart failure, acute pulmonary edema); (2) inability to comply with treatment, such as patients with severe trauma, burns, cancer undergoing chemotherapy, pregnant or lactating women, and those with mental illness; (3) withdrawal from treatment or transfer to another facility within 24 hours of admission.
 |
| Treatment plan      | 
Both groups were managed according to the 2021 Surviving Sepsis Campaign (SSC) International Guidelines for septic shock resuscitation, including: (1) early antimicrobial therapy, (2) vasopressor support (with norepinephrine as first-line), and (3) organ function support. The key difference between groups lay in the fluid resuscitation monitoring approach (critical care ultrasound vs. noninvasive cardiac output monitoring)
   |
| efficacy evaluation | 
The main efficacy indicators: emergency department length of stay, total hospital stay.
 
Secondary efficacy indicators: regarding total fluid volume within the first 6 hours of resuscitation, early resuscitation efficacy (time to achieve mean arterial pressure <math>\geq</math>65 mmHg, lactate reduction <math>\geq</math>20% from baseline, or lactate clearance <math>\geq</math> 10%), complication rates (including pulmonary edema, renal injury, and acute respiratory distress syndrome).
   |

|                           |  |
|---------------------------|--|
|                           | Safety evaluation index: 28-day mortality.   |

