| statistical method | 
This study adopted a prospective randomized controlled design, and the sample size was estimated using PASS 15.0 software. Based on the difference in 6-hour fluid resuscitation volume between the two groups in the pilot study (mean difference 1261 mL, standard deviation 3155 mL), <math>\alpha=0.05</math> (bilateral) was set <math>\beta=0.2</math>. Calculated to require 27 cases per group, considering a 20% dropout rate, 60 cases were ultimately included. Use SPSS 26.0 to generate block random sequences (block size 4), and allocate concepts through sealed envelopes. The normality of the measurement data was confirmed by Shapiro Wilk test, and those that conform to the normal distribution were expressed as mean <math>\pm</math> standard deviation. Independent sample t-test was used for inter group comparison; non normally distributed individuals are represented by the median (interquartile range) and Mann Whitney U test is used. The categorical data is presented in terms of the number of cases (%), and the comparison between groups is conducted using the chi square test or Fishers exact test (when the theoretical frequency is less than 5). The main outcome (28 day mortality rate) was plotted using Kaplan Meier survival curve, and inter group differences were analyzed using log rank test, and HR (95% CI) was calculated. Secondary outcomes (such as fluid dosage, MAP, etc.) report mean difference (MD) or relative risk (RR) and their 95% confidence intervals. All tests are bilateral, and <math>P<0.05</math> is considered statistically significant. Perform Bonferroni correction on secondary outcomes (<math>\alpha=0.05/6 \approx 0.008</math>). Multivariate Cox regression was used to adjust for confounding factors such as age and baseline lactate, and sensitivity analysis included protocol set (PP) and intention to treat (ITT) analyses. The statistical software used is R 4.3.1 (R Foundation) and SPSS 26.0 (IBM).
 |

|                        |                        |
|------------------------|------------------------|
| Research period | July 2023 to July 2025 |
|------------------------|------------------------|

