## **(1)Research background**

Septic shock represents the severe phase of infection-induced systemic inflammatory response syndrome (SIRS), characterized by a complex pathophysiological mechanism. It is primarily manifested as vasodilation, capillary leakage, and myocardial depression triggered by SIRS, with persistent hypotension, tissue hypoperfusion, and multiple organ dysfunction resulting from insufficient effective circulating blood volume as the main clinical features. With a mortality rate exceeding 40%, it ranks among the common critical illnesses in the emergency department. International guidelines for the management of septic shock highlight that early goal-directed fluid resuscitation is the cornerstone of septic shock treatment. It aims to alleviate the systemic damage caused by shock by rapidly restoring effective circulating blood volume and increasing tissue oxygen delivery, thereby improving prognosis and enhancing quality of life. Consequently, fluid resuscitation holds an irreplaceable role in the management of septic shock, and the first 6 hours after shock recognition, in particular, is designated as the "golden resuscitation period" . However, both excessive and insufficient fluid resuscitation may exacerbate the condition and elevate the risk of complications such as pulmonary edema, acute respiratory distress syndrome (ARDS), and acute kidney injury (AKI). Thus, how to rapidly and accurately assess a patients volume status and cardiac function in the emergency department, formulate individualized fluid resuscitation strategies, achieve precise volume management, and avoid over-resuscitation or under-resuscitation has become an urgent clinical challenge.

Traditional fluid resuscitation strategies rely predominantly on static parameters such as central venous pressure (CVP), mean arterial pressure (MAP), and urine output for guidance. However, these indices have inherent limitations in assessing volume responsiveness and predicting fluid resuscitation efficacy, failing to accurately and dynamically reflect a patients volume status or cardiac preload responsiveness. In recent years, with advances in hemodynamic monitoring technologies, dynamic evaluation of volume responsiveness has emerged as a key strategy for optimizing fluid resuscitation and improving patient outcomes.

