## **(3) Research Design Types, Principles, and Test Procedures**

### **1. Research Design**

Subjects were recruited from patients with septic shock admitted to the Emergency Department of Guangzhou Panyu District Central Hospital between July 2023 to July 2025. Demographic data of patients, including gender, age, and underlying diseases, were collected, along with mean arterial pressure, baseline lactate levels, and vital signs at enrollment. Records were made of the total fluid volume administered within the first 6 hours after patients were randomized into groups, the achievement of resuscitation targets,

blood lactate levels, blood pressure, and the incidence of complications such as pulmonary edema and renal injury. Additionally, the use of vasoactive agents (e.g., dopamine, epinephrine/norepinephrine), mechanical ventilation support, and antibiotics was documented. Patients were followed up to record the duration of emergency department stay, total hospital stay, 28-day mortality, and adverse events occurring during the study period (e.g., severe arrhythmias, anaphylactic shock).

After patients met the inclusion criteria and signed the informed consent form, random numbers were generated using SPSS 26.0 statistical software to randomly assign 73 participants to the critical care ultrasound group and the non-invasive cardiac output group. The generated random allocation table was prepared in duplicate, which were sealed and stored by the statistician and research coordinator respectively to prevent premature disclosure of group allocation information.

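### The protocol names conflicting primary outcomes (length of stay or 28-day mortality) and takes its sample size from 6-hour fluid volume, which it never makes primary

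*Protocol*

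**What the plan says.** The protocol ranks its outcomes in three places.

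- **Synopsis, efficacy evaluation row.** "The main efficacy indicators: emergency department length of stay, total hospital stay". Fluid volume comes next: "Secondary efficacy indicators: regarding total fluid volume within the first 6 hours of resuscitation". The row ends with "Safety evaluation index: 28-day mortality".
- **Section (7), standards for efficacy appraisal.** "The primary outcome was 28-day mortality", followed by "Secondary outcomes included the efficacy of initial resuscitation, duration of hospital stay, incidence of complications, and other relevant parameters".
- **Statistics text, in the synopsis and again in section (10).** "The main outcome (28 day mortality rate) was plotted using Kaplan Meier survival curve", with a log-rank test and a hazard ratio. Fluid dosage is given as an example of a secondary outcome.

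The same statistics text bases the sample size on the pilot difference in 6-hour fluid volume: 1261 mL, SD 3155 mL, two-sided alpha 0.05 and beta 0.2. It reports 27 per group and 60 in total after 20% dropout. It then applies a Bonferroni threshold of 0.05/6 to the secondary outcomes, without naming the six.

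**The concern.** A confirmatory comparison needs one outcome, fixed in advance, that decides the result. Here hospital stay is main in one place and secondary in another, mortality is both primary and a safety index, and the number of patients was derived from a third outcome.

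Two things are at stake. First, the label sets the significance threshold, because only secondary outcomes carry the 0.05/6 correction. With conflicting labels in force, the lead outcome could be chosen after the results are known. Second, the stated 80% power belongs to no outcome called primary. It was computed at 0.05 for an outcome that the same paragraph calls secondary and so tests at about 0.008.

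**Working it through.** **1. Outcome ranks side by side**

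| Outcome | Synopsis, efficacy row | Section (7) | Statistics text (synopsis and section 10) |
|---|---|---|---|
| ED length of stay | main | not named separately | not named |
| Total hospital stay | main | secondary | not named |
| 28-day mortality | safety index | primary | main |
| 6-hour fluid volume | secondary | not named | secondary, but the basis of the sample size |

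No outcome holds the same rank wherever it is ranked and is also the one used for sizing.

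**2. The plan's own sample size**

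Inputs (section 10): difference 1261 mL, SD 3155 mL, two-sided alpha 0.05, power 80%, 1:1 allocation. The standardised difference is d = 1261/3155 = 0.400.

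n per group = 2 × (1.960 + 0.842)² / d² ≈ 98.3, so 99 (100 by t-test). The stated 27 is not reproduced. By t-test, power at alpha 0.05 is:

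- 24 per group (30 less 20% dropout): 27%
- 27 per group: 30%
- 30 per group: 33%
- 36 and 37 per group (if 73 are randomised): 39%
- 100 per group: 80%

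**3. What the label does to the threshold**

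0.05/6 = 0.0083. Take any effect that a t-test detects with 80% power at 0.05. With 30 per group that is d = 0.736, and its power at 0.0083 is 55%. With 27 per group it is d = 0.777, again 55%. So even if the stated 80% for fluid volume were right, it would become 55% at the threshold that applies. On the protocol's own inputs (d = 0.400), power at 0.0083 is about 11% with 27 per group and 13% with 30.

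**4. Power for mortality at these sizes**

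The protocol gives no expected mortality effect. Its background section says only "With a mortality rate exceeding 40" per cent, with no time point. I assume 40% in one arm and reductions of 10 or 20 points. Because section (3) says "randomly assign 73 participants to the critical care ultrasound group and the non-invasive cardiac output group" while the synopsis and section (10) say 60, I show both totals.

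- Two proportions: power = Φ[(|p1 − p2| − 1.96 × SE0)/SE1], where SE0 is the pooled and SE1 the unpooled standard error.
- Log-rank (Schoenfeld): power = Φ[√(deaths/4) × |ln HR| − 1.96], with HR = ln(1 − p2)/ln(1 − 0.40), which is 0.698 for 30% and 0.437 for 20%.
- CI half-width for the risk difference, both arms at 40%: 1.96 × √[0.24 × (1/n1 + 1/n2)].

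| Per arm | 40% vs 30%: proportions / log-rank | 40% vs 20%: proportions / log-rank | Deaths expected (10-point / 20-point) | CI half-width |
|---|---|---|---|---|
| 24 | 11% / 11% | 32% / 35% | 16.8 / 14.4 | 28 points |
| 30 | 12% / 13% | 39% / 42% | 21 / 18 | 25 points |
| 36 and 37 | 14% / 15% | 46% / 49% | 25.5 / 21.8 | 22 points |

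With 50% in the higher arm and 30 per arm, two-proportion power is about 12% for a 10-point and 35% for a 20-point reduction.

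**The case against.** The best defence is that main efficacy indicators and primary outcome are different labels: the synopsis keeps efficacy and safety lists apart, and mortality heads the trial as a whole. This fails. Section (7) is itself headed as the standard for judging efficacy, and there it makes mortality primary and hospital stay secondary. The synopsis also disagrees with itself, its efficacy row against its statistics row.

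Sizing a trial on an outcome other than the primary can be legitimate when it is stated and justified. Here it is neither.

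Some cautions about the numbers stand:

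- The mortality powers rest on an assumed 40% rate and assumed reductions.
- The 55% for hospital stay illustrates the threshold change under a t-test. The protocol gives no effect or SD for stay, and would use Mann-Whitney if the data are not normal.
- The 55% for fluid volume is conditional on the stated 80%, so the 11% to 13% from the stated inputs is the more realistic figure.

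The failure of 27 per group to follow from its inputs and the 60-versus-73 discrepancy are separate defects. They enter here only because they affect the power that must be restated. None of this touches the contradiction, which needs no calculation.

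**Conclusion.** The concern holds and must be fixed. The current text gives conflicting answers on which outcome decides the trial, and it sizes the trial on another outcome that it calls secondary.

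Hospital stay is judged at 0.05 under the synopsis. Under section (7) it is judged at about 0.008, provided it is among the six secondary outcomes. Mortality, the outcome with most textual support as primary, has log-rank power of about 11% to 49% across the sizes and reductions shown, assuming 40% in one arm. Fluid volume does not have its stated 80% on the stated inputs: it has about 33% at 0.05 with 30 per group, and less at the secondary threshold. The contradiction itself rests on no assumption.

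**What to change.** Name one primary outcome in identical words in the synopsis efficacy row, the synopsis statistics row, section (7) and section (10), before any outcome data by arm are seen. If such data have been seen, disclose and date the change.

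- **If 28-day mortality is kept:** move ED stay and total hospital stay to the secondary family, state that the trial was not sized for mortality, and report the hazard ratio or risk difference with its 95% CI as an estimate.
- **If 6-hour fluid volume is made primary:** place mortality and both stays in the secondary family and restate the power. The stated inputs need about 100 per group, and 30 per group gives about 33%.
- **If length of stay is preferred:** choose one of the two stays, or give a multiplicity rule for both, and state the effect and SD assumed, since the protocol has neither.

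In every case, list the secondary outcomes by name, set the Bonferroni divisor to their number, and give the power for the number randomised once 60 and 73 are reconciled.

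The cost is amendment wording, with no extra patients or data unless the sponsor chooses to enlarge the trial. The sponsor gives up the freedom to pick the lead outcome later and must publish a much less favourable power than 80%.
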